## **2.) Description of Study**

The goal of this study is to investigate the role of central neural pathways in mediating chronic pain. The aim of the study is to test the effect of stimulating brain regions that are part of a network underlying central pain processing using a non-invasive brain stimulation technique, transcranial Direct Current Stimulation (tDCS). Prior studies have used tDCS to target both sensory related cortical areas (Fregni 2006) and those important for higher-order representations of pain (Mendonca 2011). This study will target brain regions important for the behavioral response to the chronic sensation of pain. The hypothesis is that stimulation of these brain regions can modulate not only the affective component of pain, but ultimately also improve functioning and quality of life. This hypothesis will be tested by treating study participants eighteen and older with chronic low back pain (CLBP) of greater than six months using tDCS. To be part of this study, participants must meet all the inclusion and exclusion criteria.

### **A. Specific Aims**

The aim of the proposed study is to determine effects of tDCS on the affective and behavioral component of chronic pain. The study will specifically target the dorsal anterior cingulate cortex (dACC), an important component of brain circuits that mediate learning in response to emotionally charged experiences. Measures of distress will be obtained due to the sensory component of pain to assess the degree to which pain interferes with the participants' daily activities, and the emotional impact of CLBP on their lives.

**Aim 1** To test the acute effects of active vs. sham cathodal (inhibitory) tDCS over dorsal anterior cingulate cortex (dACC), a region implicated in the affective components of pain in twenty (20) patients in a controlled design.

#### **Hypothesis: Acute Effect**

##### **Hypothesis 1.1**

Distress associated with pain as measured by the West Haven-Yale Multidimensional Pain Inventory (WHYMPI) (affective subscale) and pain anxiety symptom scale (PASS-20) will decrease after ten (10) days of active but not sham stimulation.

##### **Hypothesis 1.2**

Pain-related avoidance and disability measured on WHYMPI (interference subscale), PASS-20, and Rolland-Morris Disability Questionnaire (RMDQ) will decrease after ten (10) days of active but not sham stimulation.

##### **Hypothesis 1.3**

The perceptual component of pain, measured with the Defense & Veterans Pain Rating Scale (DVPRS) will not change

**Aim 2** To test the longer term effects of active vs. sham cathodal (inhibitory) tDCS over dACC in the same twenty (20) patients in a controlled design.

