**Hypothesis 2.3**

The perceptual component of pain, measured with the DVPRS will not change.

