Multiple interconnected brain regions are implicated in pain processing (Mackey 2004; Borsook 2010). These include areas of the brain directly responsible for processing sensory input such as the thalamus, primary and secondary somatosensory cortices, and regions important for mediating cognitive aspects of pain processing, such as dorsolateral prefrontal cortex (DLPFC), dorsal anterior cingulate cortex (dACC), medial and ventromedial prefrontal (mPFC and vmPFC, respectively), orbitofrontal (OFC), and insular cortex. The investigators will target those brain regions that play a role in emotional salience of pain processing. Specifically, our initial efforts will inhibit the activation of dACC. We posit that reducing the activity in dACC will decrease the emotional saliency of pain, impacting the degree to which CLBP causes disability.

The role of anterior cingulate cortex (ACC) in mediating pain processing is well supported. First, a mainstay treatment for chronic pain includes opioid medications. Though these medications act in multiple brain regions, ACC exhibits one of the highest densities of opioid receptors in the brain and is a primary site of action for these treatments (Vogt 1995). Second, selective surgical lesion of the cingulate cortex has been used to treat chronic pain since the 1960s. Importantly, following surgery, though patients reported still experiencing the pain, they were less bothered by it (Eisenberger 2004; Folzt 1968). This response supports the role of ACC in the affective component

Date most recently revised (m/d/y): 03/03/2015

Protocol Version (if applicable): 5.0

of pain processing. It is the goal of this study to determine whether a similar dissociation between the sensation of pain and the distress related to pain can be elicited by stimulating dACC using a non-invasive method, tDCS.

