### **C3. Specific Procedures or Treatments**

After the potential participant signs the consent form, is screened, found eligible and states they are still interested they will be enrolled into the study.

**Questionnaires:** Table 1, below identifies the schedule for when the study questionnaires will be used. All questionnaires will be done with assistance of blinded study personnel.

Date most recently revised (m/d/y): 03/03/2015

Protocol Version (if applicable): 5.0

**Pain Severity:** This study will use the 11-point numerical scale <http://www.dvcipm.org/files/manuals-resources/dvprs.pdf> for rating pain intensity developed by the Office of the Army Surgeon General Pain Management Task Force (2010). 0 indicates no pain and 10 indicates the most severe pain. This will be administered on screening, before and after each treatment session, and at follow-up.

**Pain Interference:** Two measures will be used to assess pain interference. First, the West Haven-Yale Multidimensional Pain Inventory (WHYMPI) (Kerns 1985) will be used as a measure of the chronic pain experience. The interference sub-scale will be used to measure perceived interference of pain in vocational, social/recreation, and family/marital functioning. Second, we will use the Rolland-Morris Disability Questionnaire (RMDQ) to assess disability specific to back pain (Roland & Morris 1983). The RMDQ is widely used and has acceptable psychometric properties (Roland & Fairbank 2000).

**Pain Acceptance:** We will assess pain acceptance with the Chronic Pain Acceptance Questionnaire-8 (CPAQ-8) (Fish et al 2010). This measure addresses the ability to experience ongoing pain but continue engaging in enjoyable daily activities that are not focused on avoiding or reducing the pain. This measure has good psychometric properties (Rovner et al. 2014)

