#### C4. Data Analysis

The PI(s) will be responsible for and supervise data collection and data management. Data will be stored in a locked cabinet in the PI's office. Data analysis will be conducted using standard statistical software including SPSS and R. Data will be analyzed through linear models including (M)ANOVA, repeated measures analyses and mixed linear model procedures to deal with correlational effects. This will be followed by appropriate post-hoc analyses comparing specific conditions. In order to maintain anonymity in data files participants will be only listed with their unique identification code. Data backup of these files and hard copies of data capture forms will be kept in locked files to which only authorized study personnel will have access. Descriptive data will be provided for all participants (e.g., mean age, sex, education, etc.). Clinical rating scales will be scored as they are in clinical use. There is no power analysis as this is an exploratory study.

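### Hypotheses 1.3 and 2.3 predict unchanged DVPRS pain intensity, but section C4 gives no criterion by which data could support that prediction

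*Combined protocol and SAP*

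**What the plan says.** Under Aim 1, Hypothesis 1.3 states that pain perception, "measured with the Defense & Veterans Pain Rating Scale (DVPRS) will not change". Under Aim 2, Hypothesis 2.3 repeats it: "The perceptual component of pain, measured with the DVPRS will not change". The companion Hypothesis 1.1 says distress "will decrease after ten (10) days of active but not sham stimulation", so it carries both a time and a comparison. Hypothesis 1.3 carries neither in its own sentence.

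Section B (Background) makes the pairing the goal of the study: to determine "whether a similar dissociation between the sensation of pain and the distress related to pain can be elicited by stimulating dACC".

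On analysis, section C4 says: "Data will be analyzed through linear models including (M)ANOVA, repeated measures analyses and mixed linear model procedures to deal with correlational effects". Unspecified post-hoc comparisons follow. It adds: "There is no power analysis as this is an exploratory study". It gives no margin, equivalence test, interval rule or significance level.

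On measurement, section C3 says of the DVPRS: "This will be administered on screening, before and after each treatment session, and at follow-up". The post-stimulation rating is also given a use of its own, the detection of immediate relief.

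**The concern.** A dissociation has two halves: distress falls, and pain sensation does not. The second half is a claim of no effect. The models in C4 will yield an estimate and an interval for the DVPRS, but the plan does not say what result would count as support for that half.

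Without such a criterion, an inconclusive DVPRS comparison and truly unchanged pain look the same. Suppose distress improves on active stimulation and the DVPRS comparison is merely non-significant. The study could then not say whether stimulation acted on affect alone or on pain intensity as well, which is the question posed in the Background.

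**Working it through.** **Inputs from the documents.** 10 participants per arm (C1); a 0 to 10 rating (C3, Pain Severity); 1 + 2 × 10 + 1 = 22 scheduled DVPRS ratings per participant. There is no power figure to reproduce.

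**Assumptions, because the documents give none.** SD of one rating 1.5, 2.0 or 2.5 points, equal in both arms; correlation r with the Session 1 rating of 0.5 to 0.7 (0.3 as a weaker case for follow-up); two-sided 5% test; margins of 1, 1.5 and 2 points; 8 per arm as a dropout case.

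**Step 1: one unadjusted rating, 10 per arm.** SE = SD × √(2/10); 95% half-width = t(0.975, 18) × SE = 2.101 × SE; noncentrality for a true 2-point difference = 2/SE.

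| SD | SE | Half-width | Noncentrality | P(non-significant) |
|---|---|---|---|---|
| 1.5 | 0.671 | 1.41 | 2.98 | 0.195 |
| 2.0 | 0.894 | 1.88 | 2.24 | 0.438 |
| 2.5 | 1.118 | 2.35 | 1.79 | 0.605 |

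With 8 per arm (14 df) the last column becomes 0.301, 0.539 and 0.680.

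**Step 2: adjusted for the Session 1 rating** (simulated ANCOVA, 40,000 trials per case, 10 per arm). The probability that a true 2-point difference is non-significant, for SD 1.5/2.0/2.5, is 0.120/0.348/0.525 at r = 0.5 and 0.034/0.184/0.366 at r = 0.7.

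**Step 3: what an interval rule would deliver.** The claim is made when the 90% interval lies wholly inside ± margin. Residual SD = SD × √(1 − r²), 17 df, t(0.95, 17) = 1.740. For SD 2, the half-width at the true residual SD is 1.740 × 1.732 × √0.2 = 1.35 at r = 0.5, and 1.740 × 1.428 × √0.2 = 1.11 at r = 0.7. Probability of the claim when the true difference is zero:

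| Case | Margin 1 | Margin 1.5 | Margin 2 |
|---|---|---|---|
| SD 2, r 0.3 | 0.002 | 0.110 | 0.456 |
| SD 2, r 0.5 | 0.007 | 0.201 | 0.595 |
| SD 2, r 0.7 | 0.045 | 0.459 | 0.826 |
| SD 2, r 0.5, 8 per arm | 0.003 | 0.104 | 0.419 |
| SD 2, r 0.7, 8 per arm | 0.021 | 0.292 | 0.686 |

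At a 2-point margin and r 0.5 to 0.7, the range is 0.902 to 0.982 for SD 1.5 and 0.279 to 0.552 for SD 2.5. Simulated ANCOVA, which allows for chance baseline imbalance, gives slightly lower values (SD 2, r 0.5 to 0.7: 0.005 to 0.036, 0.169 to 0.418 and 0.555 to 0.795).

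**Step 4: what the text already fixes.**
- *Contrast:* Aims 1 and 2 compare active with sham.
- *Baseline:* C3 (Study Visits) calls the Session 1 battery, taken before stimulation and including the DVPRS, the baseline.
- *Time points:* Table 1 puts the DVPRS in the same Session 1, Sessions 5 and 10, and six-week columns as the distress scales.
- *Still open:* the DVPRS is taken before and after stimulation at Session 10. C3 does not say which rating serves Hypothesis 1.3, or on which side of stimulation the Session 10 distress scales fall.

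**Step 5: why the contrast is worth restating.** If both arms fall equally by 1.5 points (SD 2), the SD of change is 2 × √(2(1 − r)) = 2.00 at r = 0.5 or 1.55 at r = 0.7. A paired t-test within the active arm (9 df, noncentrality 2.37 or 3.06) is then significant in 56% or 78% of trials, although active minus sham is truly zero.

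**The case against.** The strongest reply is that this is a declared exploratory study of 20 people whose Specific Aims centre on the affective and behavioural components of pain. Hypotheses 1.1, 1.2, 2.1 and 2.2 test those components and do not depend on the DVPRS. Nothing in the documents says a non-significant DVPRS result will be taken as proof of no change. Unadjusted figures also overstate the problem, since C4 allows repeated-measures and mixed models, and every SD and correlation here is assumed. Much of this stands. It limits the weight of the point, and it is why the adjusted figures are shown beside the unadjusted ones. It does not supply a criterion. C4 uses the exploratory label only to explain the absent power analysis, and even the adjusted miss rates reach 18% to 35% at SD 2.

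A reader might infer more: that Hypothesis 1.3 leaves both the rating and the contrast undefined among 22 candidates. The documents do not support that. Read with the Aims, Table 1 and the Session 1 baseline, the natural meaning is active versus sham, Session 10 (or six weeks) against Session 1. The within-arm reading in Step 5 is the less natural one.

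A reader might also infer that the trial needs a formal equivalence test or a larger sample. Step 3 shows that such a test would rarely succeed at this size unless the margin is about 2 points, so estimation is the sensible default.

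**Conclusion.** The point holds in this form: two hypotheses predict no change, the Background relies on that prediction, and C4 has no rule by which data could support it. With 10 per arm, a non-significant DVPRS comparison would miss a true 2-point difference in about 20% to 60% of trials unadjusted. The adjusted range is 12% to 53% at correlation 0.5 and 3% to 37% at 0.7, over SDs of 1.5 to 2.5. These figures illustrate scale under assumed SDs and correlations; they do not correct any number in the plan. The gap in definition is narrow: the Session 10 rating before or after stimulation, plus a contrast that should be stated in the hypothesis itself. The distress and disability hypotheses are unaffected. The change should be made, because the dissociation could otherwise be claimed on inconclusive data.

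**What to change.** **Hypotheses 1.3 and 2.3.** Name the quantity as the active-minus-sham difference in the Session 10 DVPRS (1.3) and in the six-week DVPRS (2.3), each adjusted for the Session 1 pre-stimulation rating. State whether the Session 10 rating precedes or follows stimulation, and take it at the same point as the Session 10 distress scales.

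**Section C4.** Add that:
- the DVPRS difference is reported with its confidence interval and, by default, described as an estimate;
- non-significance is not read as no change;
- no difference from sham in pain intensity, and hence (given a distress effect) dissociation, is claimed only if the 90% interval lies wholly inside a margin justified before data are seen;
- otherwise the result is called inconclusive.

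**Cost.** Wording only; every rating is already scheduled. The sponsor must justify a margin or settle for a descriptive estimate. With 10 per arm the claim will often be inconclusive: its probability is about 1–5%, 20–46% and 60–83% at margins of 1, 1.5 and 2 points (SD 2, correlation 0.5–0.7, all assumed), and lower after dropout or with a weaker correlation at follow-up. The rule supports no difference from sham, not unchanged pain within the active arm, so within-arm change is best reported descriptively. The Session 10 rating involves a trade-off: before stimulation it follows only nine treatments; after stimulation it follows all ten but also picks up any immediate relief.

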#### **Hypothesis: Longer Term Effect**

##### **Hypothesis 2.1**

Date most recently revised (m/d/y): 03/03/2015

Protocol Version (if applicable): 5.0

Distress associated with pain as measured by the WHYMPI (affective subscale) and PASS-20 will remain decreased at follow-up.

**Hypothesis 2.2**

Pain-related avoidance and disability measured on WHYMPI (interference subscale), PASS-20, and RMDQ will remain decreased at follow-up.

**Hypothesis 2.3**

The perceptual component of pain, measured with the DVPRS will not change.

**B. Background**

Chronic pain is one of the single most challenging problems facing medicine. Costs associated with treating chronic pain and the resulting disability may exceed the combined cost of treating patients with coronary artery disease, cancer, and AIDS (Turk 2002). Of patients with chronic pain, the most prevalent syndrome is CLBP. Current treatments for CLBP consist mostly of opioid and non-steroidal anti-inflammatory medications that have been largely unsuccessful in curbing the growing societal cost of pain syndromes and providing long-term relief for patients. In the study proposed, the study investigators will test the efficacy of a novel approach to modulating brain areas important for processing the emotional dimension of pain.

Recent studies of chronic pain have suggested that the sensation of pain can give rise to maladaptive avoidance behavior, and it is these behaviors that contribute to a significant part of pain-related disability. It has been posited that an adaptive mechanism exists for avoiding activities that result in further sensation of pain. In the short-term, this mechanism may protect a person from further injury. Continued avoidance of potential pain triggers, however, ultimately results in avoidance and discontinuation of daily activities that provide positive life experience, needed physical activity, and social support. This pattern of behavior ultimately leads to continued physical deconditioning, social isolation, and depressed mood (Crombez 2012), factors contributing to a higher risk of anxiety, depression, and suicide. In this study, we propose stimulation of brain regions underlying the emotional component of pain, with the goal of interrupting the continuation and reinforcement of this cycle of maladaptive behavior.

Multiple interconnected brain regions are implicated in pain processing (Mackey 2004; Borsook 2010). These include areas of the brain directly responsible for processing sensory input such as the thalamus, primary and secondary somatosensory cortices, and regions important for mediating cognitive aspects of pain processing, such as dorsolateral prefrontal cortex (DLPFC), dorsal anterior cingulate cortex (dACC), medial and ventromedial prefrontal (mPFC and vmPFC, respectively), orbitofrontal (OFC), and insular cortex. The investigators will target those brain regions that play a role in emotional salience of pain processing. Specifically, our initial efforts will inhibit the activation of dACC. We posit that reducing the activity in dACC will decrease the emotional saliency of pain, impacting the degree to which CLBP causes disability.

The role of anterior cingulate cortex (ACC) in mediating pain processing is well supported. First, a mainstay treatment for chronic pain includes opioid medications. Though these medications act in multiple brain regions, ACC exhibits one of the highest densities of opioid receptors in the brain and is a primary site of action for these treatments (Vogt 1995). Second, selective surgical lesion of the cingulate cortex has been used to treat chronic pain since the 1960s. Importantly, following surgery, though patients reported still experiencing the pain, they were less bothered by it (Eisenberger 2004; Folzt 1968). This response supports the role of ACC in the affective component

Date most recently revised (m/d/y): 03/03/2015

Protocol Version (if applicable): 5.0

of pain processing. It is the goal of this study to determine whether a similar dissociation between the sensation of pain and the distress related to pain can be elicited by stimulating dACC using a non-invasive method, tDCS.

Transcranial direct current stimulation, or tDCS, is classified by the FDA as a minimal risk technique. tDCS applies low amplitude direct current to the scalp to modulate the excitability of underlying cortex. Several studies have shown promising results treating acute pain, neuropathic pain resulting from spinal cord injury, and chronic pain from fibromyalgia (Antal 2008; Lefaucher 2008; Fregni 2006). As in these studies, tDCS will be used to target areas of the brain that participate in pain processing at higher levels beyond simply relaying sensory information. By changing activity in the “affective tier” of brain networks implicated in responses to pain, the investigators expect to modify emotional responses and behaviors that add to its burden.

## **C. Experimental Method**

### **C1. Brief Description of Subjects**

Participants will be aged over 18 years old with a diagnosis of chronic low back pain based on the inclusion criteria (see below) by a referring physician. Participants will be of any racial or ethnic group and of either sex. A questionnaire will be administered to screen for possible contraindications for tDCS (see exclusion criteria). We will consent up to thirty (30) volunteers with a goal of enrolling twenty (20) participants, ten (10) in the treatment group and ten (10) in the control group.

### **C2. Study Design**

The study includes a screening visit, ten (10) study treatment session visits on consecutive weekdays and a follow-up phone call, approximately six (6) weeks after the last study visit. The ten study visits will occur at Butler Hospital and will take between two (2) to two and half hours (2 ½) hours. The total duration of this study for the participant is expected to be up to approximately twenty- four (24) hours; this includes the consent process, screening and eligibility assessments and ten research visits which will include the study treatment, tDCS, completion of study related questionnaires, and the follow-up phone call.

Half of the participants will receive only sham stimulation for all treatment days (days where tDCS is applied) and half will receive only active stimulation; this will be randomly assigned. Comprehensive measures of distress resulting from CLBP will be administered to assess both the short and longer term effects of tDCS treatment. Participants and research staff administering outcome scales will be blinded to active vs. sham tDCS.

### **C3. Specific Procedures or Treatments**

After the potential participant signs the consent form, is screened, found eligible and states they are still interested they will be enrolled into the study.

**Questionnaires:** Table 1, below identifies the schedule for when the study questionnaires will be used. All questionnaires will be done with assistance of blinded study personnel.

Date most recently revised (m/d/y): 03/03/2015

Protocol Version (if applicable): 5.0

**Pain Severity:** This study will use the 11-point numerical scale <http://www.dvcipm.org/files/manuals-resources/dvprs.pdf> for rating pain intensity developed by the Office of the Army Surgeon General Pain Management Task Force (2010). 0 indicates no pain and 10 indicates the most severe pain. This will be administered on screening, before and after each treatment session, and at follow-up.

**Pain Interference:** Two measures will be used to assess pain interference. First, the West Haven-Yale Multidimensional Pain Inventory (WHYMPI) (Kerns 1985) will be used as a measure of the chronic pain experience. The interference sub-scale will be used to measure perceived interference of pain in vocational, social/recreation, and family/marital functioning. Second, we will use the Rolland-Morris Disability Questionnaire (RMDQ) to assess disability specific to back pain (Roland & Morris 1983). The RMDQ is widely used and has acceptable psychometric properties (Roland & Fairbank 2000).

**Pain Acceptance:** We will assess pain acceptance with the Chronic Pain Acceptance Questionnaire-8 (CPAQ-8) (Fish et al 2010). This measure addresses the ability to experience ongoing pain but continue engaging in enjoyable daily activities that are not focused on avoiding or reducing the pain. This measure has good psychometric properties (Rovner et al. 2014)

**Emotional Distress:** Investigators will employ a battery of measures to determine the degree to which participants experience emotional distress resulting from pain. First, the affective sub-scale of the WHYMPI will be used to measure negative emotion related to pain. Second, the General Anxiety Disorder 7-item scale (GAD-7) will be used to assess general anxiety symptoms. Third, the Patient Health Questionnaire (PHQ-9) will be used to assess depressive symptoms (Kroenke 2001). The PHQ-9 is a quick self-report measure demonstrating reliability and validity in primary care settings (Spitzer 1999). Lastly, we will include the short form of the pain anxiety symptom scale (PASS-20) to measure fear and avoidance behavior related to pain (McCracken & Dhingra 2002).

**Patient Expectation and Satisfaction:** We will assess treatment credibility and patient expectations for treatment success using the Credibility Expectancy Questionnaire (CEQ; Devilly & Borkovec 2000). The Client Satisfaction Questionnaire-8 (CSQ-8; Larsen, Attkisson, Hargreaves, & al., 1979), an 8-item scale, will be used at post-treatment to assess patient satisfaction with the treatment. This scale has acceptable psychometric properties (Nguyen, Attkisson, & Stegner, 1983).

**Psychiatric History:** Drug related problems, exclusionary disorders, and other non-exclusionary psychiatric disorders will be assessed with a structured psychiatric interview, the Mini International Neuropsychiatric Interview (MINI). This is a validated interview designed to screen for Axis I disorders. Potential participants that are determined by the MINI to have lifetime diagnoses of bipolar disorder, schizophrenia, other chronic psychotic condition(s), and/or drug or alcohol dependence will be considered screen failures.

Date most recently revised (m/d/y): 03/03/2015

Protocol Version (if applicable): 5.0

**Sleep Measure:** An in-office assisted report of sleep will be used to assess quantity and quality of sleep throughout the ten testing days of the study. The questions used to assess sleep have been based on those used in the 1992 Carskadon Sleep-Wake Diary.

*Table 1. Schedule of Assessments*

	Purpose	Consent and Screen	First Day of Week One Session 1	Pre/Post Treatment Session 1-10	End of Week One and Two Session 5 & 10	Six Week Follow-up
Pain Severity Defense & Veterans Pain Rating Scale (DVPRS)	I, O	X	X	X	X	X
Pain Interference WHY-MPI RMDQ	O O		X X		X X	X X
Pain Acceptance CPAQ-8	O		X		X	X
Emotional Distress PHQ-9 (Depression) GAD-7 (Anxiety) PASS-20 (Pain related fear/avoidance)	O O O		X X X		X X X	X X X
Psychiatric History MINI	I	X				
Sleep Measure Sleep assessment	O		X	X	X	X
Patient Expectation and Satisfaction CEQ CSQ-8	T T		X X		X* X* *(only session 10)	

Assessment instruments are used for the following purposes: I= Inclusion criteria; T = Treatment Development Target Assessment; O = Outcome Measure

Links to the measures, when available:

[DVPRS](#)

Date most recently revised (m/d/y): 03/03/2015

Protocol Version (if applicable): 5.0

[WHY-MPI](#)

[RMDQ](#)

[CPAQ-8](#)

[PHQ-9](#)

[GAD-7](#)

[PASS-20](#)

[CEQ](#)

[CSQ-8](#)

**Study Visits:** All participants will be clearly directed to the building and room where the study procedures will occur prior to each visit. All study visits will occur at Butler Hospital in a research room.

On the first day of treatment, prior to the tDCS treatment, females of childbearing age will be required to have a urine pregnancy test (hCG dipstick) before any study procedures. The test will be administered by a trained member of the research staff overseen by [name] or another licensed physician. Any participants that show a positive pregnancy test will be considered a screen failure.

Participants will be asked to complete the DVPRS, WHY-MPI, RMDQ, CPAQ-8, PHQ-9, GAD-7, PASS, CEQ, CSQ-8, and the Sleep Measure. This will provide a baseline measure in regards to the sensory/perceptual component of their pain, the degree to which pain interferes with daily activity, and the emotional component of their pain.

Prior to this and each study treatment, designated research staff will assess the skin on the participant's scalp where the electrodes will be placed to assure there are no lesions, cuts, or exclusionary skin disorders. Participants will be positioned for optimal comfort on a chair, recliner or stretcher. Designated trained research staff will attach the electrodes to the participant's scalp (participants will not need to have any hair shaved) and apply the flexible rubber headband to keep them in place. (See detail below). Participants will be educated that research staff will be monitoring them continuously through a non-recording closed-circuit camera from another room or he/she will be physically present in the room to assess if they need anything or want to stop the tDCS.

The participant will then receive either the sham or active tDCS stimulation based on their random group assignment for twenty minutes (tDCS details are below). Following tDCS stimulation, only the DVPRS will be repeated. This measure will be used to determine whether immediate pain relief following stimulation occurs. Lastly, in order to monitor the effectiveness of the blind, participants will be asked to guess which treatment, active or sham, they received.

On subsequent treatment days, the DVPRS will be repeated before and after stimulation and the Sleep Measure will be repeated before stimulation. At the end of the first week of treatment, session five, in addition to the DVPRS and the Sleep Measure, the WHY-MPI, RMDQ, CPAQ-8, PHQ-9, GAD-7, and the PASS, will be repeated. During the second week, the DVPRS will again be administered before and after each treatment, and the Sleep measure will be repeated before stimulation.

On the final day of treatment, in addition to the DVPRS and the Sleep Measure, the WHY-MPI, RMDQ, CPAQ-8, PHQ-9, GAD-7, CEQ, CSQ-8, and the PASS, will be repeated.

Date most recently revised (m/d/y): 03/03/2015

Protocol Version (if applicable): 5.0

Follow-up assessments will occur by phone approximately six (6) weeks after the last tDCS treatment session and will consist of these same measures as session ten.

